2. OBJECTIVES, ENDPOINTS, AND HYPOTHESIS

2.1. Objectives and Endpoints

Objectives	Endpoints	
Primary		
• To assess the dose-response relationship of up to 3 doses of JNJ-42847922 (20, and 40 mg, with 10 mg potentially added at the interim analysis) compared to placebo as adjunctive therapy to an antidepressant drug in improving depressive symptoms in subjects with MDD who have had an inadequate response to current antidepressant therapy with a selective serotonin reuptake inhibitor (SSRI) or serotonin-norepinephrine reuptake inhibitor (SNRI).	Change from baseline to the end of Week 6 in the MADRS total score.	
To assess the safety and tolerability of JNJ-42847922 compared to placebo as adjunctive therapy to an antidepressant in subjects with MDD.	• Safety assessments, including adverse events, laboratory values, ECG, vital signs, physical exam, the C-SSRS, the Arizona Sexual Experiences Scale (ASEX), and the Physician Withdrawal Checklist (PWC).	

Objectives	Endpoints	
To assess the efficacy of JNJ-42847922 compared to placebo as adjunctive therapy to an antidepressant in improving depressive symptoms in subjects with MDD with significant insomnia symptoms (baseline Insomnia Severity Index [ISI] score ≥15) versus those without significant insomnia symptoms (baseline ISI score <15).	 Correlation between baseline ISI score as a continuous variable and change from baseline to the end of Week 6 in the MADRS total score. Change from baseline to the end of Week 6 in the MADRS total score in subjects with baseline ISI score ≥15 versus subjects with baseline ISI score <15. Shift in ISI score category from baseline to the end of Week 6. 	
To assess the efficacy of JNJ-42847922 compared to placebo as adjunctive therapy to an antidepressant in improving: Response and remission of depressive symptoms	 Proportion of responders on depressive symptoms scale, defined as a ≥50% improvement in MADRS total score from baseline to the end of Week 6. Proportion of subjects with remission of depressive symptoms, defined as a MADRS total score ≤8, ≤10, or ≤12 at the end of Week 6. 	
- Anxiety symptoms	 Change from baseline to the end of Week 6 on the 14-item Hamilton Anxiety Rating scale (HAM-A) total score. 	
Response of anxiety symptoms	 Proportion of responders on anxiety symptoms scale, defined as a ≥50% improvement in the HAM-A total score from baseline to the end of Week 6. 	
- Clinical severity	 Change from baseline to the end of Week 6 in the Clinical Global Impression-Severity (CGI-S) score. 	
 Global functioning (work/school, social and family life). 	 Change from baseline to the end of Week 6 in the Sheehan Disability Scale (SDS). 	
To assess the efficacy of JNJ-42847922 compared to placebo as adjunctive therapy to an antidepressant in improving depressive symptoms in the subpopulation of subjects with MDD with anxious distress.	Change from baseline to the end of Week 6 in the MADRS total score in subjects with MDD with anxious distress versus subjects with MDD without anxious distress.	
To evaluate the effect of JNJ-42847922 exposure on the HPA axis in subjects with MDD.	• Change from baseline to Weeks 2, 4, and 6 in salivary cortisol levels, as measured upon awakening.	

Objectives	Endpoints	
To assess the exposure of JNJ-42847922 and metabolites M12 and M16 in subjects with MDD.	Observed plasma concentrations of JNJ-42847922 and metabolites and estimated exposure parameters for JNJ-42847922 from population based PK modeling.	
To capture patient-reported assessment of JNJ-42847922 compared to placebo as adjunctive therapy to an antidepressant.	 Change from baseline to the end of Week 6 in: Depressive symptoms using the Patient Health Questionnaire 9-item (PHQ-9) Anhedonia using the Snaith-Hamilton Pleasure Scale (SHAPS) Sleep disturbance using the Patient Reported Outcome Measurement Information System-Sleep Disturbance (PROMIS-SD) Short Form Fatigue using the PROMIS-Fatigue Short Form Severity of depression using the Patient Global Impression-Severity (PGI-S) Health related quality of life and utility using the European Quality of Life (EuroQol) Group, 5-Dimension, 5-Level (EQ-5D-5L) questionnaire Work productivity and limitations using the Work Limitations Questionnaire (WLQ) Short Form. 	

In addition, the exploratory objectives are:

- To identify diagnostic biomarkers and to investigate changes in MDD-related biomarkers (HPA axis function, biomarkers of immune system activation and oxidative stress) in relation to clinical response on depression symptoms upon adjunctive treatment with JNJ-42847922
- To explore the exposure/response relationship of JNJ-42847922 in subjects with MDD
- To identify genetic factors that may influence the PK, safety, or tolerability of JNJ-42847922
- To assess the predictive capability of salivary cortisol levels assessed during the circadian nadir (predose in the evening) on the antidepressant effect of JNJ-42847922.

Refer to Section 9, Study Evaluations for evaluations related to endpoints.

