The efficacy of study drug will be evaluated using the MADRS (SIGMA version), HAM-A (SIGH-A version), CGI-S, SDS, PHQ-9, SHAPS, PROMIS-SD (Short Form), PROMIS-Fatigue (Short Form), PGI-S, EQ-5D-5L, and WLQ (Short Form). The Ruminative Response Scale (RRS) will be collected at baseline only, and will be evaluated as a potential predictor of treatment outcome.

PHARMACOKINETIC EVALUATIONS

Sparse blood samples will be collected for measurement of plasma concentrations of JNJ-42847922 and the active metabolites M12 and M16. These data will be used for population PK analysis of JNJ-42847922, and if necessary, analysis of metabolites M12 and M16.

Post-hoc Bayesian estimates of PK parameters will be obtained for JNJ-42847922 from population PK modeling (and, if needed, for M12 and M16) and may be used in exploratory exposure-response analysis.

BIOMARKER EVALUATIONS

Saliva samples for the measurement of cortisol concentrations will be collected by using an oral swab method just before bedtime (before dosing) on the night before each visit and upon awakening on the day of the visits during the double-blind treatment phase. In addition, salivary cortisol samples will be collected at the study site at baseline (before study drug administration on Day 1) and prior to each blood sample for PK on Days 1, 2, and 8 (note: samples on Days 1 and 2 will only be collected from those subjects participating in the Day 1 overnight stay). If a subject does not participate in the overnight stay on Day 1, then the cortisol samples on Days 1 and 2 will not be collected.

Venous blood samples for the assessment of biomarkers related to the immune system activity, growth factors, metabolic, and HPA axis activation will be collected on each visit during the double-blind phase. Biomarkers may be added or deleted based on scientific information or technical innovations under the condition that the total volume of blood collected will not be increased.

PHARMACOGENOMIC AND EPIGENETIC (DNA) EVALUATIONS

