Any secondary efficacy endpoint which is defined as a change from baseline will be analyzed using the same MMRM as for the primary efficacy endpoint, with the corresponding baseline as a covariate. The secondary endpoint analyses will not be controlled for Type I error and nominal p-values will be presented.

Pharmacokinetic Analysis

Concentration-time data will be graphically displayed by dose, visit date and time (relative to dose) for JNJ-42847922, M12, and M16 and summarized using descriptive statistics.

A population PK analysis using PK data from a selection of Phase 1 and Phase 2 studies will be performed at the completion of the study and at the interim analysis. Using actual sampling and dosing times, concentration-time data will be analyzed using population PK modeling. Post-hoc Bayesian estimates of PK parameters (ie, area under the concentration-time curve [AUC] and, if allowed by the data, maximum drug concentration [C_{max}]) will be obtained for JNJ-42847922 from population PK modeling, and if necessary, for M12 and M16. As part of the population PK modeling, the effect of intrinsic (eg, age, gender, body weight) and extrinsic factors (eg, concomitant medications) affecting the PK of JNJ-42847922 may be evaluated if needed. Individual predicted plasma concentration-time profiles and/or post-hoc Bayesian estimates of PK parameters for JNJ-42847922 and, if necessary, for M12 and M16 may be used for exploratory exposure-response modeling for safety and efficacy endpoints.

Biomarker Analysis

Cortisol levels will be tabulated for each time point and summary statistics will be calculated. Posttreatment changes in cortisol levels will be assessed by treatment group. Analysis of variance (ANOVA) and t-test will be used to assess differences across groups and time points. Correlations between cortisol levels and clinical endpoints will be evaluated.

The additional exploratory biomarkers will be tabulated by treatment and summary statistics will be calculated. Posttreatment changes in exploratory biomarkers will be summarized by treatment group. Associations between baseline biomarker levels and clinical endpoints may be explored.

Pharmacogenomic Analysis

Individual predicted post-hoc Bayesian estimates of PK parameters will be used in exploratory exposure-genetic variant modeling, as appropriate.

Safety Analyses

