- h. The clinical laboratory assessments (including TSH, hematology, serum chemistry, HbA1c, lipid panel, and urinalysis) should be performed under fasting conditions (with the possible exception of screening laboratory tests).
- i. FT₄ analysis will be performed for subjects with known hypothyroidism who have been on stable treatment for at least 3 months prior to screening and otherwise for any subject with an elevated TSH.
- j. A urine sample will be collected and sent to the central laboratory to assess compliance with the following background antidepressant medications: citalopram, escitalopram, fluvoxamine, fluoxetine, paroxetine, sertraline, and venlafaxine. All other SSRI/SNRI background antidepressants qualifying the subject for enrollment will be assayed (urine or blood sample) locally at the study site, if possible.
- k. Subjects will administer the assigned study drug once daily at bedtime, approximately 3 hours after the last meal, from Day 1 to Day 41. Subjects are required to record the administration of study drug or any missed doses in subject diaries, which will be checked at each scheduled visit.
- 1. As this is a blinded study, blood samples for PK will be collected from placebo-dosed subjects, but not analyzed for PK. These samples will be stored and may be analyzed if needed (eg, suspicion of an incorrect dose).
- m. Pharmacogenomic and epigenetic blood samples will be collected only from subjects who have consented to provide optional DNA samples for research.
- n. To avoid interference caused by lipid content in morning blood specimens collected for biomarker evaluation, biomarker samples will be collected under fasting conditions.
- o. Start date (first day) of last menstrual period and average length of menstrual cycle (days) will be collected from premenopausal women.
- p. Salivary cortisol samples (morning and evening) will be collected by subjects at home. Evening salivary cortisol samples (ie, on Days -1, 7, 21, and 41) will be collected predose, at bedtime. The morning sample will be collected upon awakening (ie, on Days 1, 8, 22, and 42). Subjects should not consume alcoholic beverages for at least 12 hours prior to saliva sampling. Food, drinks (except water), and oral care (brushing, flossing, mouthwash) are not permitted 1 hour prior to the saliva collection.

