9.4. Biomarkers Evaluations

Venous blood samples will be collected for the assessment of biomarkers as indicated in the Time and Events Schedule. To avoid interference caused by lipid content in blood specimens collected for biomarker evaluation, biomarker samples will be collected under fasting conditions (for a minimum of 8 hours, water permitted).

Saliva samples for the measurement of cortisol concentrations will be collected by using an oral swab method just before bedtime (before dosing) on the night before each visit and upon awakening on the day of the visits indicated in the Time and Events Schedule. In addition, salivary cortisol samples will be collected at the study site at baseline (before study drug administration on Day 1) and prior to each blood sample for PK on Days 1, 2, and 8 (Note: samples on Days 1 and 2 will only be collected from those subjects participating in the Day 1 overnight stay). (Note: order of samples: salivary cortisol followed by biomarker blood samples and then PK samples; exact time of all samples should be recorded). Cortisol concentration has a strong diurnal pattern, with peak concentrations present upon awakening and low concentrations in the evening hours. Collection of saliva cortisol samples (which correlate well with serum concentrations) allows for collection at home with a low subject burden. Subjects should not consume alcoholic beverages for at least 12 hours prior to saliva sampling. Food, drinks (except water), and oral care (brushing, flossing, mouthwash) are not permitted 1 hour prior to the saliva collection.

Biomarker analyses will include (but are not limited to) markers related to the immune system activity, growth factors, metabolic, and HPA axis activation, to allow for exploratory assessment of drug-clinical response relationship, to explain interindividual variability in clinical outcomes, and to identify population subgroups that respond differently to treatment.

Biomarkers may be added or deleted based on scientific information or technical innovations under the condition that the total volume of blood collected will not be increased.

All biomarker data obtained during this study may be included in ongoing cross-study analyses to investigate the relationship between depression severity and phenotypes and biomarkers.

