11.5. Biomarker Analysis

Cortisol levels will be tabulated for each time point and summary statistics will be calculated. Posttreatment changes in cortisol levels will be assessed by treatment group. Analysis of variance (ANOVA) and t-test will be used to assess differences across groups and time points. Correlations between cortisol levels and clinical endpoints will be evaluated.

The additional exploratory biomarkers will be tabulated by treatment and summary statistics will be calculated. Posttreatment changes in exploratory biomarkers will be summarized by treatment group. Associations between baseline biomarker levels and clinical endpoints may be explored. Additional exploratory analyses may also be performed. Results of all exploratory analysis will be presented in a separate report.

All biomarker data obtained from this study may also be included in an ongoing cross-study analysis to investigate the relationship between depression severity, phenotypes, and biomarkers.

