#### **Baseline RRS Score**

The RRS consists of 22 items which are rated on 4-point Likert scales ranging from "almost never" to "almost always". The total score is calculated as the sum of the 22 items.

Subjects will be dichotomized based on their baseline RRS score to evaluate whether there are differences in these subgroups (i.e., evaluating change from baseline to the end of Week 6 in the MADRS total score in subjects with RSS score  $\geq$ the median versus subjects with RRS score <median). Descriptive statistics of the change from baseline to the end of Week 6 in the MADRS total score will be presented by treatment group for these subgroups.

In addition, the correlation between baseline RRS score as a continuous variable and change from baseline to the end of Week 6 in the MADRS total score will be evaluated by means of a scatter plot and if appropriate, regression analysis.

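### The only analysis stated for whether evening cortisol predicts the drug's effect is a correlation with clinical endpoints, which cannot separate a prognostic marker from one that modifies the drug-placebo difference

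*Protocol*

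**What the plan says.** Protocol 2.1 lists as an exploratory objective: "To assess the predictive capability of salivary cortisol levels assessed during the circadian nadir (predose in the evening) on the antidepressant effect of JNJ-42847922". SAP 1.1 repeats it. Protocol 2.2 frames the drug's effect on depressive symptoms as superiority to placebo. Protocol 9.4 gives, among the purposes of the biomarker work, "to identify population subgroups that respond differently to treatment".

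On method, Protocol 11.5 has three relevant sentences:

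- Cortisol against outcome, repeated in the synopsis: "Correlations between cortisol levels and clinical endpoints will be evaluated".
- Cortisol as an outcome in its own right: "Analysis of variance (ANOVA) and t-test will be used to assess differences across groups and time points".
- For the additional exploratory biomarkers: "Associations between baseline biomarker levels and clinical endpoints may be explored".

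SAP Sections 1 and 8 leave biomarker analyses to a separate document. The SAP's amendment history records that the cortisol-efficacy association analysis was moved to a biomarker SAP.

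The samples needed are scheduled. Footnote p of the Time and Events Schedule states: "Evening salivary cortisol samples (ie, on Days -1, 7, 21, and 41) will be collected predose, at bedtime".

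The RRS is collected at baseline and, according to the synopsis and Protocol 3.1 and 3.2, "will be evaluated as a potential predictor of treatment outcome". Its analysis is in the available SAP. Section 5.2.3.5 splits subjects at the median and gives descriptive statistics of Week 6 MADRS change by treatment group. It then examines "the correlation between baseline RRS score as a continuous variable" against that change, with a scatter plot and regression if appropriate.

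**The concern.** The antidepressant effect of the drug is a contrast with placebo. A baseline marker predicts that effect only if the contrast changes with the marker, which is a marker-by-treatment interaction. A correlation between cortisol and MADRS change measures something else: whether people with higher cortisol improve more or less, whatever they receive. A marker tied to the course of the episode equally on drug and on placebo yields a clear correlation and says nothing about who benefits from the drug.

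At stake is whether this objective gets an answer. If the correlation is all that is produced, a finding could be read as evidence about who responds to the drug when it is only evidence about prognosis. For the RRS the gap is narrower: the by-arm statistics let a reader compare drug with placebo in each half of the sample, but provide no estimate or interval for how far the two contrasts differ.

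**Working it through.** **Basis in the plan.** Protocol 11.2 gives 280 randomized, 25% dropout, a difference of 4.5 MADRS points, SD 10 and one-sided 0.05. Protocol 3.1 gives 2:1:1 initial allocation. Evaluable subjects: 280 × 0.75 = 210, or 105 placebo, 52.5 on 20 mg and 52.5 on 40 mg.

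**The plan's own figure.** With the three candidate shapes of SAP 5.2.3.1 (no 10 mg arm), Monte Carlo power is 84.1% (linear), 92.5% (Emax) and 81.8% (exponential). The mean is (84.1 + 92.5 + 81.8)/3 = 86.1%, against the stated approximately 85%. This supports 210 as the working sample size. No figure is stated for the cortisol analysis, and the point does not rest on the power figure.

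**Assumptions not in the documents.** Marker standardised and complete; active doses pooled (105 against 105); tests two-sided at 0.10, to match the 90% CIs the SAP uses for pairwise comparisons. The protocol states no test, level or pooling rule for these correlations.

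**Model.** Y = −4.5·T + ρ·10·X + γ·T·X + error, with T = 1 for active, X the marker, and error SD 10·√(1 − ρ²). A purely prognostic marker has γ = 0. There were 6,000 runs per setting.

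| Truth | Pooled correlation significant | Active-only correlation significant | Interaction test significant |
|---|---|---|---|
| ρ = 0, γ = 0 | 9% | 10% | 10% |
| ρ = 0.1, γ = 0 | 41% | 28% | 10% |
| ρ = 0.2, γ = 0 | 90% | 67% | 10% |
| ρ = 0.3, γ = 0 | nearly 100% | 93% | 10% |
| ρ = 0, γ = 2 | 40% | 65% | 43% |
| ρ = 0, γ = 3 | 66% | 91% | 69% |
| ρ = 0, γ = 4.5 | 92% | nearly 100% | 94% |

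The pooled correlation fires about equally often for a weak prognostic marker (ρ = 0.1, 41%) and for a pure modifier of 2 points per SD (40%), so it cannot say which is present. Restricting it to active subjects does not help.

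**Hand check at two-sided 0.05.** Fisher z power = Φ(atanh(r)·√(n − 3) − 1.96).

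- n = 210, √207 = 14.39. r = 0.1: 1.44 − 1.96 = −0.52, 30%. r = 0.2: 2.92 − 1.96 = 0.96, 83%. r = 0.3: 4.45 − 1.96 = 2.49, 99%.
- n = 105, √102 = 10.10. The same r values give 17%, 54% and 88%.

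**Precision of the interaction.** SE of the slope difference = 10·√(1/105 + 1/105) = 1.38 points per SD of marker. The 90% CI half-width is 1.645 × 1.38 = 2.27. The slope difference detectable with 80% power is (1.645 + 0.842) × 1.38 = 3.43, about 3.4 points per SD.

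**The case against.** The strongest reply is that the governing cortisol plan has not been seen. Protocol 11 describes itself as general, Protocol 11.5 allows further exploratory analyses, and the SAP hands biomarkers to a separate document, which may contain an interaction model. This stands. The conclusion has to be about what the protocol states, not about everything that is planned. It does not dispose of the point, since the protocol sets the objective and names only a correlation for it.

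A reader might infer that the correlation will ignore placebo, or that a prognostic marker will be reported as predictive. The documents support neither. They do not say whether correlations are pooled, by arm or active-only, and they give no rule for calling cortisol predictive. By-arm correlations with placebo shown would be informative, though still without an interval for the difference.

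A reader might also infer that Phase 3 would be enriched for high cortisol or high rumination. The synopsis and Protocol 1.2 say the results will be used to select doses and endpoints; enrichment is not mentioned.

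On the RRS, predicting treatment outcome is looser wording than predicting the drug's effect, and a correlation partly fits it. The median split by treatment group includes placebo, so the contrast can be read in each stratum, and regression is allowed if appropriate. All of this stands; only the estimate and interval for the difference are missing.

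Finally, the interaction is imprecise: a detectable change of 3.4 points per SD is large beside an assumed total effect of 4.5. That is true, but it is a limit of the data, and an interval reports it openly.

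**Conclusion.** The point holds in limited form. For the evening cortisol objective, the protocol states only a correlation, which by itself cannot distinguish prognosis from modification of the drug-placebo difference. Whether the separate biomarker SAP already deals with this is unknown. For the RRS, the SAP gives a descriptive contrast with placebo but no estimate or interval for the difference in effect.

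The simulated rates illustrate the ambiguity and do not forecast a false claim. They depend on assumed within-arm correlations of 0.1 to 0.3, pooled doses, complete marker data and a significance test the plan does not set. The logical point needs none of these.

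The cortisol objective is exploratory and the trial is declared non-confirmatory. Nothing here touches the primary or secondary conclusions. It is a cheap improvement worth making.

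**What to change.** In Protocol 11.5, and in the biomarker SAP if it is not already there, name the analysis for this objective. Add baseline (Day -1) evening cortisol and its interactions with treatment and time to the MADRS MMRM of SAP 5.2.3.1, with placebo included. Report the Week 6 active-minus-placebo difference in slope with a 90% CI, and state whether doses are pooled for that contrast. Do the same for continuous baseline RRS in SAP 5.2.3.5. Keep the correlations, scatter plots and median-split tables as descriptive output, and reserve the word *predictive* for the interaction.

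If the biomarker SAP already contains such a model, Protocol 11.5 needs only a cross-reference, and the RRS change remains.

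The cost is a few lines of text. No new data are needed: the Day -1 evening sample is scheduled without regard to arm, the RRS is collected at baseline, and the model exists. The downside is wide intervals, about ±2.3 MADRS points per SD of marker under the assumptions above, and wider if cortisol samples are missing.
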